#### On-Chart LogMAR

On-chart LogMAR eyes are defined as having a value of 20/800 or better (i.e. 1.6 LogMAR).

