## Additional Responder Definitions

### Eye Responder

#### Criteria 1

Responder will be defined as an eye that loses less than or equal to +0.2 LogMAR. Early discontinuations will be considered as non-responder for both eyes.

#### Criteria 2

Responder will be defined as an eye that loses less than or equal to +0.3 LogMAR. Early discontinuations will be considered as non-responder for both eyes.

#### Criteria 3

Responder will be defined by an improvement of at least -0.2 LogMAR compared to baseline. Early discontinuations will be considered as non-responder for both eyes.

#### Criteria 4

Responder will be defined by an improvement of at least -0.3 LogMAR compared to baseline. Early discontinuations will be considered as non-responder for both eyes.

#### Criteria 5

Responder will be defined by an improvement of at least -0.4 LogMAR compared to baseline. Early discontinuations will be considered as non-responder for both eyes.

#### Criteria 6

Responder will be defined by an improvement of at least -0.5 LogMAR compared to baseline. Early discontinuations will be considered as non-responder for both eyes.

#### Criteria 7

Responder will be defined as an eye that has 20/200 or better visual acuity. Early discontinuations will be considered as non-responder for both eyes.

Criteria 8

Responder will be defined as an eye that has better than 20/200 visual acuity. Early discontinuations will be considered as non-responder for both eyes.

Criteria 9

Responder will be defined as an eye whose improvement of HVF Parameters (Mean deviation or Foveal Sensitivity) from baseline is at least 1 time the coefficient of repeatability. Early discontinuations will be considered as non-responders.

Criteria 10

Responder will be defined by an improvement of at least +0.2 LogCS compared to baseline. Early discontinuations will be considered as non-responder for both eyes.

Criteria 11

Responder will be defined by an improvement of at least +0.3 LogCS compared to baseline. Early discontinuations will be considered as non-responder for both eyes.

Criteria 12

Responder will be defined for the eyes which were On-Chart eyes at baseline and which have an improvement of at least -0.2 LogMAR or which were Off Chart at baseline but became On Chart with at least 5 ETDRS letters at a particular visit

Criteria 13

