## **5.7 HANDLING OF MISSING DATA AND/OR INVALID DATA AND OUTLIERS**

### **5.7.1 Efficacy**

If a subject's visual acuity is light perception and no LogMAR can be assigned, then a LogMAR value of 4 will be assigned. If a subject's visual acuity is no light perception, then a LogMAR value of 4.5 will be assigned.

In case of missing data at Week 48, the following rules will be applied in the primary imputation method:

Rule 1: If the LogMAR is available at the previous and the following visits then the imputed value at Week 48 will be a linear interpolation of LogMAR.

Rule 2: If there is no following visit due to drop out then the relative change ( $RC_i$ ) from visit  $V_i$  to visit  $V_{i+1}$  will be calculated at each visit from the baseline to the visit preceding Week 48 in the group treated with a sham. The last available visit ( $V_i$ ) with data ( $X_i$ ) will be used as the starting time point. The imputed score at  $V_{i+1}$  for each eye will be equal to  $X_{i+1} = X_i + X_i * RC_i$ . The imputed score at the next missing visit  $V_{i+2}$  will be equal to  $X_{i+2} = X_{i+1} + X_{i+1} * RC_{i+1}$ , and so on up to Week 48 visit. The  $RC_i$  will be the same for the treated and sham eyes.

With the primary method of imputation, the between eye difference at Week 48 will be proportional to the between eye difference at the time of withdrawal because the same RCi coefficients are used for both eyes.

The secondary imputation method leading to an additional sensitivity analysis will apply the same Rule 1 but Rule 2 will be based on the evolution of the difference between treated and sham eye. RCi is then the relative change from visit i to visit i+1 of the difference between treated and sham eye in all subjects attending visit i and i + 1.

Other:

When a test result score/value for the Pelli-Robson Contrast test, or the Farnsworth-Munsell 100 Hue Color test is missing at any visit, for the reason that the subject was unable to perform because the vision was too poor or unable to perform within the constraints of time limitation pre-defined in the Standard Operating Procedure (for the Farnsworth-Munsell 100 Hue Color test), the following convention will be utilized: the worst possible score for the given test will be utilized as the value for that visit.

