#### Primary Analysis for EMA

The null and alternative hypotheses for the primary endpoint are defined below

$$H_0: \mu_{\text{All-GS010}} = \mu_{\text{All-Sham}}$$

$$H_1: \mu_{\text{All-GS010}} \neq \mu_{\text{All-Sham}}$$

Where  $\mu$  presents the mean change from baseline to Week 48 in LogMAR. “All” represents all eyes treated with GS010 or Sham

The primary analysis will be performed on the ITT population. The change from baseline to Week 48 in the LogMAR acuity will be the primary response. The change from baseline of all-GS010 eyes will be compared to the change from baseline of all-Sham eyes (intra-subject comparison) using a mixed model of analysis of covariance (ANCOVA) using the following terms (or covariate) in the model:

- Subject as random factor
- Eyes of the subject as random factor,
- Treatment and the
- Baseline LogMAR for each eye.

The analysis will be performed based on alpha of 0.05. The statistical significance in favor of GS010 against sham will provide evidence of the advantage of using GS010 for halting visual acuity loss or improving visual acuity in subjects with LHON with duration of vision loss of 6 months or less. The difference in the mean change from baseline (adjusted mean difference) to Week 48 between the two treatment groups and associated 95% confidence interval will be reported.

The center will not be included in the analysis as the number of subjects recruited per site will be very small. However, stratification by geographical area will be performed as a sensitivity analysis. Neighboring countries can be pooled together to reach at least 9 subjects per geographical entity. The pooling will be performed during the masked review of data.

All the model diagnostics will be checked.

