#### Sensitivity Analyses

The primary analysis with the same model will be repeated for the following lists.

- 1) Per protocol
- 2) Randomized subjects even if they were not treated and assigned treatment by randomization instead of actual treatment received
- 3) Secondary handling of missing data
- 4) Model with geographical area effect
- 5) Model excluding major outliers if any
- 6) Analysis of absolute Week 48 LogMAR values
- 7) Baseline GCL thickness/volume
- 8) Best or worst-seeing eye (eye status) added as a binary covariate
- 9) Duration of vision loss at the time of Screening added as a covariate in the model

All these analyses will be presented in a forest plot displaying treatment effect, 95% confidence intervals and p-value. The analysis will also be presented in tabular format.

- 10) Non-parametric Analysis: Wilcoxon signed-rank test will be performed as a sensitivity analysis to compare between all-GS010 eyes and all-Sham eyes
- 11) On-chart eyes at baseline
- 12) Off-chart eyes at baseline
- 13) Analysis of absolute Week 48 LogMAR values for on-chart eyes at baseline
- 14) On-chart eyes at baseline and per protocol population
- 15) On-chart eyes at baseline and all randomized subjects
- 16) On-chart eyes at baseline and Secondary handling of missing data
- 17) On-chart eyes at baseline and Duration of vision loss at the time of Screening added as a covariate in the model
- 18) On-Chart eyes at baseline and at Week48, Week 72 and Week 96
- 19) Off-Chart eyes at baseline and at Week48, Week 72 and Week 96

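### SAP sensitivity items 18 and 19, on their natural reading, select eyes by chart status at follow-up; that status is a cut of the outcome, so their treatment estimates are biased

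*SAP*

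**What the plan says.** SAP section 9.5.1, Sensitivity Analyses (EMA), opens: "The primary analysis with the same model will be repeated for the following lists". Item 18 is "On-Chart eyes at baseline and at Week48, Week 72 and Week 96" and item 19 is "Off-Chart eyes at baseline and at Week48, Week 72 and Week 96". The FDA list has the same two items under the same numbers. In both lists, items 11 and 12 already select on baseline status alone; item 11 reads "On-chart eyes at baseline".

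The response is fixed under Primary Analysis for EMA: "The change from baseline to Week 48 in the LogMAR acuity will be the primary response". Both primary models adjust for baseline LogMAR. The EMA model is a mixed ANCOVA over all eyes with subject and eye as random factors. The FDA model is an ANCOVA on best-seeing eyes, compared between subjects.

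Chart status is defined in SAP section 5.6 by acuity: "On-chart LogMAR eyes are defined as having a value of 20/800 or better (i.e. 1.6 LogMAR"). The same section also gives a letters-read definition, which is again an acuity result. Responder criteria 12 and 13 count as a success an eye "which were Off Chart at baseline but became On Chart with at least 5 ETDRS letters at a particular visit". For an eye reduced to light perception with no LogMAR assignable, section 5.7.1 says "then a LogMAR value of 4 will be assigned".

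SAP section 9.5.3 makes everything other than the primary analysis supportive. No rationale, estimand or caveat is given for items 18 and 19.

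**The concern.** Whether an eye is on-chart at Week 48 depends on its Week 48 LogMAR, the quantity being compared. If GS010 preserves acuity, item 18 keeps borderline GS010 eyes and drops the sham eyes that did worst, including any scored 4 for light perception. Item 19 does the reverse: it drops the eyes that recovered enough to read the chart, which the SAP elsewhere calls responders. In both cases membership depends on treatment, so randomisation no longer protects the comparison.

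At stake is how the result is read. The items are labelled sensitivity analyses of the primary endpoint, so a smaller or reversed estimate would look like evidence that the effect is not robust, and a larger one like confirmation. Neither inference would be sound.

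**Working it through.** **1. The plan's own figure.** SAP section 3.3 gives a difference of 0.3 LogMAR, an SD of the between-eye difference in change of 0.594, 36 subjects and 84% power. The standardised difference is 0.3/0.594 = 0.505, and the noncentrality is 0.505 × √36 = 3.03. A two-sided 0.05 paired t-test then has 83.8% power, so the figure reproduces. The documents state no figure for items 18 and 19.

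**2. Inputs.** From the documents: effect -0.30 LogMAR, cut at 1.6, baseline-adjusted model, between-eye SD 0.594. If changes in the two eyes correlate ρ, the per-eye SD is 0.594/√(2(1−ρ)), which is 0.42 at ρ = 0 and 0.594 at ρ = 0.5. Assumed, because the documents do not give them: baseline LogMAR mean 1.2, SD 0.4; mean sham decline 0.2 to 0.5; normal errors; the same effect in every eye; selection at Week 48 only.

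**3. Hand check at one baseline value.** For an eye with mean μ and SD σ at Week 48, the mean among eyes at or below 1.6 is μ − σφ(k)/Φ(k), with k = (1.6 − μ)/σ. Take baseline 1.2, decline 0.2 and σ = 0.42.
- Sham: μ = 1.4, k = 0.476, φ/Φ = 0.356/0.683 = 0.521; selected mean 1.4 − 0.42 × 0.521 = 1.181.
- GS010: μ = 1.1, k = 1.190, φ/Φ = 0.196/0.883 = 0.222; selected mean 1.1 − 0.42 × 0.222 = 1.007.
- Difference: 1.007 − 1.181 = -0.174, against a true -0.30.

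**4. Simulation over the baseline distribution, ANCOVA adjusted for baseline, item 18.** Selecting on baseline alone gives -0.30 in every setting.

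| Mean decline | Per-eye SD | Item 18 estimate | Shrinkage |
|---|---|---|---|
| 0.2 | 0.42 | -0.208 | 0.092/0.30 = 31% |
| 0.2 | 0.594 | -0.180 | 0.120/0.30 = 40% |
| 0.5 | 0.42 | -0.166 | 0.134/0.30 = 45% |
| 0.5 | 0.594 | -0.145 | 0.155/0.30 = 52% |

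Of the eyes on-chart at baseline, item 18 keeps 68–88% on GS010 and 50–72% on sham. Item 19 gives -0.15 to -0.22, a shrinkage of 0.08/0.30 = 27% to 0.15/0.30 = 50%. Baseline-only selection of off-chart eyes (item 12) again gives -0.30.

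**5. Paired model with other inputs.** A within-subject model was run with baseline mean 1.3, SD 0.6 and between-eye baseline correlation 0.6; the correlation of change ran from 0 to 0.6 and the mean sham change from 0 to +0.6 (all assumed). Item 18 gives -0.173 to -0.241 and item 19 gives -0.169 to -0.255. Baseline-only selection gives -0.298 to -0.302.

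**6. No effect.** If treatment does nothing in any eye, the cut acts alike on both arms. The simulated estimate is 0.00 for both items.

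**7. Effects that differ between eyes.** Illustrative inputs, error SD 0.5. Item 18: on-chart baseline mean 1.1, SD 0.35, sham change +0.3. Item 19: baseline 2.0 or worse, sham change +0.1.
- Item 18, benefit only in eyes that would otherwise go off-chart: -0.165 without follow-up selection, +0.05 with it.
- Item 18, benefit only in eyes that would stay on-chart: -0.288 becomes -0.45.
- Item 19, only eyes near the chart recover: -0.277 becomes +0.235.
- Item 19, only the worst eyes gain and stay off-chart: -0.360 becomes -0.391.

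**The case against.** The strongest reply is that the wording is terse and may mean eyes with a given baseline chart status, analysed at Weeks 48, 72 and 96. FDA items 6 and 13 use that same list of visits as analysis times. This stands as a reason to ask which was meant. It does not remove the point: items 11 and 12 already select on baseline alone, and items 18 and 19 attach the visits to the chart status itself. A programmer following the text would select on the outcome.

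The second reply is that these analyses are supportive and carry no alpha. That is correct. The forest-plot sentence also follows items 1 to 9, so the SAP does not clearly place items 18 and 19 in that figure.

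A reader might infer three stronger things that the documents do not support.
- That the selection always biases towards zero. This holds for a roughly uniform effect; step 7 shows reversal and exaggeration otherwise.
- That broken pairing is a defect particular to these items. The FDA comparison is between subjects and has no pairing to break. In the EMA list, items 11 and 12 also select eye by eye and can drop one eye of a subject.
- That the primary conclusion is at risk. It is not.

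**Conclusion.** The point holds as a fault in two supportive analyses. On the natural reading, items 18 and 19 condition on a post-treatment outcome and give a biased, non-randomised comparison. Under a uniform -0.30 LogMAR effect, the estimate falls to about -0.15 to -0.21 (item 18) and -0.15 to -0.22 (item 19). The size rests on the assumptions in step 2; the different inputs in step 5 give somewhat less shrinkage. Selection was modelled at Week 48 only and dropout was not modelled. With no effect in any eye there is no bias. With effects that vary between eyes the direction cannot be known in advance, so the estimates cannot be used as robustness evidence either way. The primary test and its alpha are unaffected.

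**What to change.** Delete items 18 and 19 from both lists as sensitivity analyses of the treatment effect. If baseline chart status analysed at Weeks 48, 72 and 96 was intended, reword them to select on baseline status only; at Week 48 they then repeat items 11 and 12, so only Weeks 72 and 96 would be new.

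Report on-chart and off-chart status at each visit as an outcome, in a baseline-by-visit table per treatment. Criteria 12 and 13 already capture off-to-on conversion; the table adds loss from on-chart to off-chart.

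If the jointly selected subsets are kept, show them as descriptive summaries without a treatment-effect test. State whether all three visits are required together: SAP section 7.1 expects some subjects not to have reached Week 96 at the primary analysis, so their membership would then be unknown.

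The change must precede unmasking, because Appendix V of the protocol rules out SAP amendments once the randomisation code is broken. The cost is SAP wording only.

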#### Primary Analysis for FDA

The null and alternative hypotheses for the primary endpoint are defined below

$$H_0: \mu_{\text{best-GS010}} = \mu_{\text{best-Sham}}$$

$$H_1: \mu_{\text{best-GS010}} \neq \mu_{\text{best-Sham}}$$

Where  $\mu$  presents the mean change from baseline to Week 48 in LogMAR and “best” indicates best-seeing eyes.

The primary analysis will be performed on the ITT population. The change from baseline to Week 48 in the LogMAR acuity will be the primary response. The change from baseline of the best-GS010 eyes will be compared to the change from baseline of the best-Sham eyes (inter-subject comparison) using analysis of covariance (ANCOVA) including treatment as a main effect and baseline LogMAR as a covariate in the model. The analysis will be performed based on alpha of 0.05. The statistical significance in favor of Best-GS010 eyes against Best-sham eyes will show evidence of the advantage of using GS010 in the best eye for halting visual acuity loss or improving visual acuity in subjects with LHON with a duration of vision loss of 6 months or less. The difference in the mean change from baseline (adjusted mean difference) to Week 48 between the two treatment groups and associated 95% confidence interval will be reported.

The center will not be included in the analysis as the number of subjects recruited per site will be very small. However, stratification by geographical area will be performed as a sensitivity analysis. Neighboring regions will be pooled together to reach at least 9 subjects per geographical entity. The pooling will be performed during the masked review of data. An additional model will add the treatment by geographical area interaction to test for lack of generalizability of treatment effect.

The same analysis will be repeated for worst-GS010 eyes against worst-Sham eyes.

All the model diagnostics will be checked.

#### Secondary analysis of primary end point for FDA

Secondary Analysis of primary variable for FDA will be based on the methodology described above for primary analysis of primary variable for EMA. For secondary analysis, change of LogMAR from baseline at Week 48 will be compared between all-GS010 eyes and all-Sham eyes (intra-subject comparison). The difference in the mean change from baseline to Week 48 between the two treatment groups and associated 95% confidence interval will be reported.

#### Other Analysis

LogMAR and ETDRS score for each visit and change from baseline will be summarized by treatment group (Best-GS010/Best-Sham). LogMAR and ETDRS score for each visit and change from baseline will also be summarized by treatment group (Worst-GS010/Worst-Sham).

A graph presenting the mean of each treatment group at baseline and the mean at Week 48 will be presented. The graph will be useful to assess whether the difference in the change from baseline is mainly due to the difference at baseline or the difference at Week 48.

#### Sensitivity Analysis

Primary analysis with the same model will be repeated for the following lists.

- 1) Per protocol
- 2) Randomized subjects including those not treated
- 3) Secondary handling of missing data
- 4) Model with country effect
- 5) Model excluding major outliers if any (defined as a standardized endpoint greater than the absolute value of 4.0)
- 6) Analysis of absolute Week 48, Week 72 and Week 96 LogMAR values, without covariate adjustment
- 7) Baseline GCL layer thickness/volume
- 8) Duration of vision loss at the time of treatment as a covariate

All these analyses will be presented in a forest plot displaying treatment effect, 95% confidence intervals and p-value.

- 10) Non-parametric Analysis: Wilcoxon Rank-Sum test will be performed as a sensitivity analysis to compare between Best-GS010 eyes and Best-Sham eyes.
- 11) On-chart eyes at baseline
- 12) Off-chart eyes at baseline
- 13) Analysis of absolute Week 48, Week 72 and Week 96 LogMAR values for on-chart eyes at baseline

- 14) On-chart eyes at baseline and per protocol population
- 15) On-chart eyes at baseline and all randomized subjects
- 16) On-chart eyes at baseline and Secondary handling of missing data
- 17) On-chart eyes at baseline and Duration of vision loss at the time of Screening added as a covariate in the model
- 18) On-Chart eyes at baseline and at Week48, Week 72 and Week 96
- 19) Off-Chart eyes at baseline and at Week48, Week 72 and Week 96

### **9.5.2 Methods for Handling Dropouts and Missing Data**

Method for dealing with missing data has been detailed in [Section 5.7.1](#).

### **9.5.3 Multiplicity**

All the type I error ( $\alpha=0.05$ ) will be spent for the primary end point analysis. All the other analysis will be supportive analysis of the primary end point. Therefore, no adjustment of multiplicity will be necessary.

### **9.5.4 Pooling of Sites**

No pooling of sites will be applied for the primary analysis. However, a stratification by geographical area will be performed as a sensitivity analysis. Neighboring countries can be pooled together to reach at least 9 subjects per geographical entity. The pooling will be performed during the masked review of data.

### **9.5.5 Secondary Variables**

#### GCL thickness/volume

The change of RGC layer thickness/volume from baseline to Week 48 will be based on ANCOVA including the subject and the eyes of the subject as random factors, the treatment, and the baseline GCL thickness/volume as covariates in the model. The analysis will be performed based on alpha of 0.05. The difference in the mean change from baseline (adjusted mean difference) to Week 48 between the two treatment groups (all-GS010 vs all-Sham and best-GS010 vs best-Sham) and associated 95% confidence interval will be reported.

#### RNFL temporal quadrant and papillo macular bundle

The change of RNFL temporal quadrant and papillo macular bundle from baseline to Week 48 will be analyzed same way as GCL volume and topographical map

#### Change from baseline of the LogMAR scores at Week72/Week 96

The treatment estimate at Week 72/Week 96 will be based on the same statistical approach as the primary endpoint analysis for EMA between all-GS010 and all-Sham and Best-GS010 vs Best-Sham.

#### Time Course of the response

Time course of response will be explored in two ways:

The ANCOVA model for primary end point comparing All-GS010 and All-Sham eyes will be used for each visit for the estimation of treatment effect. The treatment effect estimate of each visit will be multiplied by -50 to convert change LogMAR to change of ETDRS letters.

Treatment estimate (LS means difference between All-GS010 and All-Sham) and associated 95% confidence interval will be plotted for each visit.

Time course analysis will compare time course of the response up to Week 48 using the mixed model procedure. The change from baseline to Week 48 in the LogMAR will be the response. The change from baseline of all GS010 eyes will be compared to the change from baseline of all sham eyes using a mixed model of repeated measure (MMRM) including the subject and the eyes of the subject as random factors, the treatment, Visit, eye status at baseline (Best or worst), interaction between eye status at baseline and treatment, interaction between visit and treatment and baseline as covariates in the model. The estimate of treatment effect at various time points and its 95%CI (without adjustment for multiplicity) will be presented. Unstructured covariance structure will be fitted. In case of any convergence problem with this covariance structure other covariance structures like compound symmetry (CS) will be used.

Three graphical presentations will be performed:

- 1) A graph with the time course of the response for the treated best eye, the sham best eye, the treated worst eye and the untreated worst eye.
- 2) A graph with the time course of the response of the treated eye (irrespective of the status at baseline) and the sham eye (irrespective of the response).
- 3) A graph with the time course of the response of the treatment effect (delta between treatment groups) for the best Seeing Eye at baseline and for the worst Seeing Eye at baseline.

In the graphs the pertinent p values including that of interaction between eye status and treatment, time effect, treatment effect, treatment by time interaction will be displayed.

Two additional analyses with the same model (excluding eye status and treatment interaction) for the best-seeing Eye and for the worst-seeing will be performed (sub-group analysis).

The same analysis will be continued for up to Week 96-time course.

All the model diagnostics will be investigated.

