12.4 Statistical Methods

12.4.1 Primary Analysis and Associated Planned Analyses

The primary analysis will be performed on the ITT subject population, which consists of all randomized and treated subjects. The change from baseline to Week 48 in the LogMAR acuity will be the primary response. The ETDRS score will not be directly used because there is a clear relationship between the mean and variance and according to Taylor's power law ($\log SD^2 = 1.743 \log mean + 0.48$, $R^2 = 0.839$) the best transformation is the logarithm (slope close to 2 and ease of interpretation of the difference in means of log). Because LogMAR is a logarithmic scale and is well known by ophthalmologists, this scale is retained as the primary one. The change from baseline of the treated eye will be compared to the change from baseline of the sham eye using a mixed model including the subject, the treatment and the baseline as covariates.

The center will not be included in the analysis as the number of subjects recruited per site will be very small. The difference in the mean change from baseline to Week 48 between the two treatment groups and associated 95% confidence interval will be reported. Alternative non parametric analysis (signed Wilcoxon test) will be performed as a sensitivity analysis to decrease the influence of possible outliers.

The treatment effect reflects well the effect on the better- and worse-seeing eye if no marked interaction between the eye status (better- versus worse-seeing) and treatment exists. To verify this hypothesis, a model including the subject as a random factor, the treatment as a fixed factor as well as the eye status (better- or worse-seeing) and the interaction between eye status and treatment will be fitted. If the P-value of the interaction test is below 0.15 a potential interaction is detected. In that case the better-seeing eye treated with GS010 will be compared to the better-seeing eye treated with sham and the worse-seeing eye treated with GS010 will be compared the worse-seeing eye treated with sham in an ANCOVA model including the LogMAR at baseline and the treatment. The study is then powered $(1-\beta=0.8)$ to detect a difference of approximately 30 letters between the two treatments.

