**Secondary Objectives:**

- To evaluate the efficacy of GS010 compared with sham over the follow-up period and at Week 96 in the change from baseline of the LogMAR.
- To verify whether the efficacy at Week 48 and at Week 96 of GS010 compared with sham and measured by the change from baseline in the LogMAR is dependent upon the treatment of the better- or worse-seeing-eye.
- To verify whether the rate of responders at Week 48 and 96 is dependent upon the treatment received and whether the magnitude of the treatment effect is dependent upon the treatment of the better- or worse-seeing eye at entry.
- To assess the effect of GS010 on parameters measured with high resolution SD-OCT
- To assess the effect of GS010 on standardized automated visual fields obtained with the Humphrey Visual Field (HVF) Analyzer II.
- To assess the effect of GS010 on contrast sensitivity measured with the Pelli-Robson chart.
- To assess the effect of GS010 on color vision measured with the Farnsworth-Munsell 100 Hue color test.

[REDACTED]

[REDACTED]

[REDACTED]

[REDACTED]

[REDACTED]

[REDACTED]

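### The one eye-status-by-treatment test in the visible SAP is averaged over visits, so it does not answer the secondary objective about Week 48 and Week 96

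*SAP*

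**What the plan says.** The SAP's secondary objectives include this one: "To verify whether the efficacy at Week 48 and at Week 96 of GS010 compared with sham", and whether that efficacy, "measured by the change from baseline in the LogMAR is dependent upon the treatment of the better- or worse-seeing-eye". Two time points are named.

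The analysis that comes closest is the mixed model for repeated measures in SAP 9.5.5, Time Course of the response. Its fixed effects are treatment, visit, eye status, baseline and two interactions: "interaction between eye status at baseline and treatment, interaction between visit and treatment and baseline as covariates in the model". The covariance is specified as "Unstructured covariance structure will be fitted", with compound symmetry named as an example of a fallback. The graphs are to show "the pertinent p values including that of interaction between eye status and treatment". For the later time point, "The same analysis will be continued for up to Week 96-time course".

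Protocol 12.4.1 places a model with eye status, treatment and their interaction inside the primary (Week 48) analysis: "If the P-value of the interaction test is below 0.15 a potential interaction is detected". Best eyes and worst eyes are then compared separately. Protocol 12.4.2 applies the primary approach again at Week 96.

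**The concern.** The MMRM lets the treatment effect change from visit to visit, but holds the best-minus-worst difference in that effect at one value for every visit. The displayed interaction p-value therefore tests a single common difference, with early visits contributing. The model to Week 96 produces a second average over more visits; it is not a Week 96 test.

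The question has practical weight. Protocol 12.4.1 says that the overall treatment effect represents both eyes only in the absence of a marked interaction. SAP 9.5.1 makes all eyes the primary comparison for EMA and best-seeing eyes the primary comparison for FDA. Whether the effect differs by eye status at Week 48 is what connects those two results. If an interaction develops late, the averaged p-value could be unremarkable and be read as showing that the effect is the same in both eyes.

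**Working it through.** **1. Is the difference tested at Week 48 or Week 96 anywhere else in the visible SAP?**

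- 9.5.1, EMA sensitivity item 8: eye status enters as a main effect only.
- 9.5.1, secondary analysis for EMA and primary analysis for FDA: best against best and worst against worst, in separate ANCOVAs at Week 48.
- 9.5.5, LogMAR at Week 72/96: all against all and best against best; worst eyes are not named.
- 9.5.5, additional time-course models: one per eye status, with the interaction removed.
- 9.5.5, eye responders: McNemar test on all eyes.

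None of these tests best against worst at a given week.

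**2. Which visits are averaged?** The SAP does not list them. Protocol 7.3.1 excludes Visit 4 (24 hours) from efficacy, so the first eligible visit is inferred to be Week 2. That gives six visits to Week 48 (2, 4, 8, 12, 24, 48) and eight to Week 96 (adding 72 and 96).

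**3. What weight does each visit get?** Let B and W be the changes in a subject's best and worst eye. If the best eye is treated, the mean of B + W includes the best-eye effect; if the worst eye is treated, it includes the worst-eye effect. The interaction is therefore the difference in mean B + W between these two groups of subjects. If it is forced to be constant over visits, generalized least squares gives visit weights

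w = R⁻¹1 / (1′R⁻¹1),

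where R is the covariance of B + W across visits. Adding a constant to all elements of R does not change w. This assumes complete data, 18 subjects per group and both eyes with the same covariance, and leaves out the baseline covariate. The documents give no covariance across visits, so three were assumed:

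| Assumed covariance | Week 48 weight, model to Week 48 | Week 96 weight, model to Week 96 |
|---|---|---|
| Compound symmetry | 1/6 = 16.7% | 1/8 = 12.5% |
| Constant variance, correlation exp(−gap/24 weeks) | 38% | 26% |
| Variance growing with time (0.4 × min(s,t)/48, plus 0.02 on the diagonal) | about 0% | about 0% |

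If a true interaction of 0.3 LogMAR exists only at the last visit, the fitted value is 0.3 × weight: 0.05, 0.115 or 0.00 in the shorter model, and 0.038, 0.077 or 0.00 in the longer one.

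**4. If the interaction builds up gradually.** Suppose that it grows linearly from zero to its Week 48 value and then stays level. With equal weights the fitted share of the Week 48 value is

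- to Week 48: (2 + 4 + 8 + 12 + 24 + 48)/(6 × 48) = 98/288 = 34%;
- to Week 96: (98/48 + 1 + 1)/8 = 51%.

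With the exponential-decay covariance the same trajectory gives 52% and 67%; with the growing variance it gives 7% in both models.

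**5. Can the reader combine the two separate models?** Not by adding their squared standard errors. Each subject gives a treated eye to one comparison and a sham eye to the other. With equal variances σ², inter-eye correlation ρ and 18 subjects per group, the variance of the difference between the two effects is (4σ²/18)(1 + ρ), against 4σ²/18 if they were independent. The SE is larger by √(1 + ρ), or 22% at an assumed ρ of 0.5. Protocol 12.2 says that this correlation is usually positive.

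**6. How precise would a single-visit contrast be?** SAP 3.3 gives an SD of 0.594 for the between-eye difference in change. As a check, 0.3/0.594 with 36 subjects gives 83.8% power by noncentral t, against the stated 84%. The SD of B + W is 0.594 × √((1 + ρ)/(1 − ρ)), and the SE of the interaction is that SD × √(2/18). With two-sided alpha 0.05 and 34 degrees of freedom:

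| Assumed ρ | SE | 95% CI half-width | Power for a 0.3 interaction |
|---|---|---|---|
| 0 | 0.198 | 0.40 | 31% |
| 0.5 | 0.343 | 0.70 | 14% |
| 0.7 | 0.471 | 0.96 | 9% |

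**The case against.** The strongest reply is that little is lost. The protocol used its interaction test as a gate to separate best-eye and worst-eye comparisons. The SAP now runs those comparisons at Week 48 unconditionally and adds a repeated-measures model for each eye status, so effects by eye status and visit will be available. The time course is described as exploratory, SAP 9.5.3 makes everything beyond the primary endpoint supportive, and a common interaction is a defensible economy with 36 subjects. A single-visit test would have low power. All of this stands, and it limits the importance of the point. It does not turn the averaged p-value into a test at Week 48 or Week 96, and two separate estimates are not a test of their difference.

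A reader might infer four stronger things that the documents do not support.

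- *That no such test is planned at all.* Protocol 12.4.1 still contains one, and no visible SAP text withdraws it. Parts of the SAP are also blacked out, so the statement is limited to the visible text.
- *That the fitted interaction is 34% or 51% of the true one.* Those figures need a linear build-up and equal weights. The SAP specifies an unstructured covariance, and neither it nor the trajectory is given.
- *That weighting by precision must lower those figures.* It can raise or lower them, as step 4 shows.
- *That the third graph, of the treatment effect over time by eye status, will show parallel curves by construction.* That follows only if it is drawn from the pooled model. The SAP does not name the source, and the separate models would impose no such constraint.

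**Conclusion.** The point holds in a limited form. In the visible SAP the only eye-status-by-treatment test is a covariance-weighted average over visits, so the secondary objective on Week 48 and Week 96 has no matching test there. The start at Week 2 is an inference. Under compound symmetry with complete data, the target visit has 1/6 of the weight in the first model and 1/8 in the second. Beyond that the size of the dilution is unknown, since it depends on a covariance and a trajectory that the documents do not give. No primary estimate or decision rests on this p-value, so it is a desirable improvement and no threat to the primary analysis.

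**What to change.** Either carry the single-visit eye-status-by-treatment model of Protocol 12.4.1 into the SAP at Week 48 and at Week 96, or add visit by eye status and visit by eye status by treatment to the MMRM. In both cases report the best-minus-worst difference in treatment effect with its 95% CI at each week. State that the third time-course graph comes from a model in which this difference may vary by visit.

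The first option needs only SAP wording and two small models. The second adds 5 + 5 = 10 fixed effects to the model to Week 48 and 7 + 7 = 14 to the model to Week 96, which is a load with about 36 subjects. The contrast is a between-subject comparison of about 18 against 18, and the half-widths above show how wide its interval may be. The SAP should therefore call it a supportive estimate and say that a non-significant p-value is not evidence of equal effects. Protocol Appendix V allows no SAP amendment after the code is broken; anything added later counts as ad hoc, so the change belongs before unmasking.
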